5.1.2 Hypotheses and Statistical Methods for Secondary Objectives

5.1.2.1 Secondary Objective 1

5.1.2.1.1 Hypotheses

Non-inferiority of MenACYW Conjugate Vaccine Compared to Menactra[®] in Terms of hSBA Vaccine Seroresponse in the Adult Population (18 to 55 Years Old)

Thirty days after the administration of MenACYW conjugate vaccine or Menactra[®], the percentages of subjects who achieve an hSBA vaccine seroresponse (as defined in Section 4.4.2.4) for meningococcal serogroups A, C, Y, and W in Groups 1b, 2b, and 3b combined are non-inferior to the corresponding percentages in Group 4b.

Null hypothesis (H₀): $p_{(G123)} - p_{(G4)} \leq -10\%$

Alternative hypothesis (H₁): $p_{(G123)} - p_{(G4)} > -10\%$

where $p_{(G123)}$ and $p_{(G4)}$ are the percentages of subjects who achieve an hSBA vaccine seroresponse in Groups 1b, 2b, and 3b pooled and Group 4b, respectively.

Each of the serogroups A, C, Y, and W will be tested separately. If the lower limit of the 2-sided 95% CI of the difference between the 2 proportions is $> -10\%$, the inferiority assumption will be rejected. The overall non-inferiority of this objective will be demonstrated if all 4 individual null hypotheses are rejected.

5.1.2.1.2 Statistical Methods

For the 4 non-inferiority hypotheses using the seroresponse rates, the CI of the difference in proportions will be computed for each of the serogroups A, C, Y, and W using the Wilson Score method without continuity correction (8). The statistical method as described in Section 5.1.1.2.2 will be used to Groups 1b - 3b pooled and Group 4b.

5.1.2.2 Secondary Objective 2

5.1.2.2.1 Hypotheses

Non-inferiority of MenACYW Conjugate Vaccine Compared to Menactra[®] in Terms of hSBA Vaccine Seroresponse in the Adolescent Population (10 to 17 Years Old)

Thirty days after the administration of MenACYW conjugate vaccine or Menactra[®], the percentages of subjects who achieve an hSBA vaccine seroresponse (as defined in Section 4.4.2.4) for meningococcal serogroups A, C, Y, and W in Groups 1a, 2a, and 3a combined are non-inferior to the corresponding percentages in Group 4a.

Null hypothesis (H₀): $p_{(G123)} - p_{(G4)} \leq -10\%$

Alternate hypothesis (H₁): $p_{(G123)} - p_{(G4)} > -10\%$

where $p_{(G123)}$ and $p_{(G4)}$ are the percentages of subjects who achieve an hSBA vaccine seroresponse in Groups 1a, 2a, and 3a pooled and Group 4a, respectively.

Each of the serogroups A, C, Y, and W will be tested separately. If the lower limit of the 2-sided 95% CI of the difference between the 2 proportions is $> -10\%$, the inferiority assumption will be rejected. The overall non-inferiority of this objective will be demonstrated if all 4 individual null hypotheses are rejected.

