
Planned Sample Size:
	
A total of 3300 subjects are planned to be enrolled:
 
 
• Group 1: MenACYW conjugate vaccine (Lot 1): planned = 900 (evaluable = 810) 
 
• Group 1a: 400 subjects 10 to 17 years of age
 
• Group 1b: 500 subjects 18 to 55 years of age
 
 
 
• Group 2: MenACYW conjugate vaccine (Lot 2): planned = 900 (evaluable = 810) 
 
• Group 2a: 400 subjects 10 to 17 years of age
 
• Group 2b: 500 subjects 18 to 55 years of age
 
 
 
• Group 3: MenACYW conjugate vaccine (Lot 3): planned = 900 (evaluable = 810) 
 
• Group 3a: 400 subjects 10 to 17 years of age
 
• Group 3b: 500 subjects 18 to 55 years of age
 
 
 
• Group 4: Menactra®: planned = 600 (evaluable = 540) 
 
• Group 4a: 300 subjects 10 to 17 years of age
 
• Group 4b: 300 subjects 18 to 55 years of age
 
 
 
 
The planned number of subjects is based on a 10% dropout rate allowing around 88% power to reject the primary hypotheses simultaneously assuming the independence between each of the endpoints.

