## 5.4 Modification of the Trial and Protocol

Any amendments to this trial plan and protocol must be discussed with and approved by the Sponsor. If agreement is reached concerning the need for an amendment, it will be produced in writing by the Sponsor, and the amended version of the protocol will replace the earlier version. All substantial amendments (e.g., that affect the conduct of the trial or the safety of subjects) require IEC / IRB approval, and must also be forwarded to regulatory authorities.

An administrative amendment to a protocol is one that modifies some administrative or logistical aspect of the trial but does not affect its design or objectives or have an impact on the subjects' safety. Administrative changes do not require IEC / IRB approval; however, the IEC / IRB must be notified whenever one is made.

The Investigator is responsible for ensuring that changes to an approved trial, during the period for which IEC / IRB approval has already been given, are not initiated without IEC / IRB review and approval, except to eliminate apparent immediate hazards to subjects.

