## **12 Statistical Methods and Determination of Sample Size**

### **12.1 Statistical Methods**

Clinical data will be analyzed under the responsibility of the Biostatistics Platform of the Sponsor. A statistical analysis plan (SAP) will be written and peer reviewed before any analyses. In accordance with the protocol, the SAP will describe all analyses to be performed under the responsibility of the Sponsor and all the conventions to be taken.

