MenACYW conjugate vaccine is an investigational vaccine that is undergoing active clinical investigation. The formulation has been evaluated in over 650 subjects (infants, toddlers, and adults > 55 years of age) in MET39 and MET44. Both the studies showed the potential of the candidate vaccine as a potent immunogen in all age groups, including young infants and older adults. The MenACYW conjugate vaccine was found to be immunogenic and well tolerated; it did not raise any safety concerns in the above trials using the final formulation or in the earlier trials. Additionally, the vaccine has been evaluated in another Phase II study in subjects aged 10 to 17 years in the US (MET50). The immunological analysis is still ongoing, however, no new safety concerns or signals have been identified to date.

The purpose of MET43 is to demonstrate the immune lot consistency of the antibody responses to meningococcal serogroups A, C, Y, and W following the administration of a single dose of MenACYW conjugate vaccine. Additionally, MET43 has the purpose of demonstrating the non-inferiority of the antibody responses to meningococcal serogroups A, C, Y, and W following the administration of a single dose of MenACYW conjugate vaccine compared to those observed following the administration of a single dose of Menactra[®]. Generation of immune lot consistency data and immune non-inferiority versus a licensed vaccine is an important regulatory requirement for registration of this vaccine.

2 Trial Objectives

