5.1.2.3.1 Hypotheses

No hypotheses will be tested. Descriptive statistics will be presented.

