5.1.4 Complementary Output

Additional analyses by age group, gender, and racial origin will be provided in Appendix 15 of the CSR.

Immunogenicity analyses:

- hSBA GMTs and 95% CI at each time point for each group – Per-Protocol Analysis Set
- Vaccine seroresponse against meningococcal serogroups A, C, Y, and W measured by hSBA and 95% CI – Per-Protocol Analysis Set
- rSBA GMTs and 95% CI at each time point for each group – Per-Protocol Analysis Set
- Vaccine seroresponse against meningococcal serogroups A, C, Y, and W measured by rSBA and 95% CI – Per-Protocol Analysis Set

Safety analyses:

- Safety overview after injection –Safety Analysis Set

Additional analyses will also be performed on SafAS2 with the following analyses:

- Safety overview after injection - Safety Analysis Set 2
- Unsolicited non-serious AEs in the six subjects at site [REDACTED] excluded from the Safety Analysis Set
- Solicited reactions in the six subjects at site [REDACTED] excluded from the Safety Analysis Set

Additional analyses will also be performed on PPAS2 and FAS2 with the following analyses:

- Equivalence of hSBA GMT against meningococcal serogroups A, C, Y, and W among 3 lots (Groups 1-3) 30 days after vaccination
- Non-inferiority of hSBA vaccine seroresponse rate for MenACYW conjugate vaccine (Groups 1-3 pooled) versus Menactra® (Group 4)
- Non-inferiority of hSBA vaccine seroresponse rate for MenACYW conjugate vaccine (Groups 1b-3b pooled) versus Menactra® (Group 4b)
- Non-inferiority of hSBA vaccine seroresponse rate for MenACYW conjugate vaccine (Groups 1a-3a pooled) versus Menactra® (Group 4a)
- Difference of hSBA vaccine seroresponse rate against meningococcal serogroups A, C, Y, and W among 3 lots (Groups 1-3)
- Comparison of the hSBA GMT for MenACYW conjugate vaccine (Groups 1-3 pooled) versus Menactra® (Group 4)

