5.5.2 Power Calculation for the Primary Objectives

[REDACTED]

[REDACTED]

[REDACTED]

[REDACTED]	[REDACTED]	[REDACTED]	[REDACTED]	[REDACTED]
[REDACTED]	[REDACTED]	[REDACTED]	[REDACTED]	[REDACTED]
[REDACTED]	[REDACTED]	[REDACTED]	[REDACTED]	[REDACTED]
[REDACTED]	[REDACTED]	[REDACTED]	[REDACTED]	[REDACTED]
[REDACTED]	[REDACTED]	[REDACTED]	[REDACTED]	[REDACTED]
[REDACTED]	[REDACTED]	[REDACTED]	[REDACTED]	[REDACTED]
[REDACTED]	[REDACTED]	[REDACTED]	[REDACTED]	[REDACTED]

[REDACTED]

[REDACTED]

[REDACTED]	[REDACTED]	[REDACTED]	[REDACTED]	[REDACTED]
[REDACTED]	[REDACTED]	[REDACTED]	[REDACTED]	[REDACTED]
[REDACTED]	[REDACTED]	[REDACTED]	[REDACTED]	[REDACTED]
[REDACTED]	[REDACTED]	[REDACTED]	[REDACTED]	[REDACTED]
[REDACTED]	[REDACTED]	[REDACTED]	[REDACTED]	[REDACTED]
[REDACTED]	[REDACTED]	[REDACTED]	[REDACTED]	[REDACTED]
[REDACTED]	[REDACTED]	[REDACTED]	[REDACTED]	[REDACTED]

[REDACTED]

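### Should the adult and adolescent non-inferiority claims depend on Primary Objective 2 being met?

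*SAP*

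**What the plan says.** Three comparisons with Menactra share one decision rule: Primary Objective 2 (all ages; SAP 5.1.1.2.1, Protocol 12.1.1.2), Secondary Objective 1 (adults; SAP 5.1.2.1.1, Protocol 12.1.2.1) and Secondary Objective 2 (adolescents; SAP 5.1.2.2.1, Protocol 12.1.2.2). In each, the lower limit of a 2-sided 95% interval must exceed -10% for every serogroup: "The overall non-inferiority of this objective will be demonstrated if all 4 individual null hypotheses are rejected". Nothing else is required.

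Secondary Objectives 3 and 4 are handled differently. SAP 5.1.2.3.1 and 5.1.2.4.1 both state "No hypotheses will be tested. Descriptive statistics will be presented". Secondary Objectives 1 and 2 are therefore formal tests.

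The sample-size text is redacted in both documents. What remains readable concerns the primary objectives: the heading "Power Calculation for the Primary Objectives" (SAP 5.5.2), and the Protocol Synopsis statement that the planned size rests on 10% dropout, "allowing around 88% power to reject the primary hypotheses simultaneously".

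**The concern.** Requiring all four serogroups controls error within one objective, but not across three objectives that each spend a full one-sided 2.5%. As written, an adult or adolescent claim can stand when the pooled comparison has failed. Calling an objective secondary ranks it but does not set a testing order. The SAP Introduction says that "immune non-inferiority versus a licensed vaccine is an important regulatory requirement for registration of this vaccine", so a reader may want the standing of each Menactra claim settled before unblinding. An apparently cheap remedy is available: one SAP sentence allowing the age-group tests only after Primary Objective 2 succeeds.

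**Working it through.** **Inputs.** Planned numbers are in the Protocol Synopsis: adults 3 × 500 = 1500 vs 300, adolescents 3 × 400 = 1200 vs 300. The stated evaluable numbers reproduce: 900 × 0.9 = 810 per lot and 600 × 0.9 = 540. Assuming the same 10% loss in each age group gives 1350 vs 270 adults, 1080 vs 270 adolescents and 2430 vs 540 pooled. The 88% power figure cannot be reproduced because its inputs are redacted. Control seroresponse rates below are assumptions in the range 0.5-0.9.

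**Test.** SAP 5.1.1.2.2: lower limit = (p123 - p4) - z·√[l123(1 - l123)/n123 + u4(1 - u4)/n4], where l123 and u4 are Wilson limits and z = 1.96. The test passes if the lower limit exceeds -0.10.

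**Error as written.** The two age groups share no subjects, so at nominal level the chance of at least one false age-group claim is 1 - 0.975² = 4.94%. Simulation with one serogroup at -10 points in both age groups, the other three certain to pass, and control rates of 0.5-0.9 gives:

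| Event | As written | Gate on Primary 2 |
|---|---|---|
| Each objective alone | 2.5-2.9% | – |
| Any false age-group claim | 5.0-5.7% | 1.6-1.9% |
| Any false Menactra claim | 5.9-6.6% | 2.5-2.8% |
| Age-group claim while Primary 2 fails | 3.4-3.8% | 0 |

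With two serogroups at the margin, any false claim as written falls to 0.2% if serogroups are independent, and to 0.6-1.4% with within-subject correlation of 0.3-0.5.

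**What the gate leaves open.** Suppose a different serogroup is at -10 points in each age group and the other age group does well enough for the pooled comparison to pass. The gate then still allows 4.9-5.7% across the two age-group claims. Joint control needs a further step. At control rates of 0.5-0.8 and differences of 0 or -2, gate plus Holm costs about 1-11 points of power. Gate plus a fixed order with adults first costs adolescents about 6-23 points.

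**What the gate costs.** Four independent serogroups, all required to pass. Control rates and true differences are given as adults/adolescents:

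| Control | Difference (points) | Claim | As written | Gated |
|---|---|---|---|---|
| 0.5/0.5 | -2/-2 | adults | 20.9% | 19.8% |
| 0.75/0.75 | 0/-5 | adults | 85% | 80% |
| 0.75/0.75 | 0/-10 | adults | 85% | 38% |
| 0.75/0.75 | -10/0 | adolescents | 81% | 13% |
| 0.7/0.8 | -2/-2 | adolescents | 59.2% | 55.7% |
| 0.5/0.8 | -2/-2 | adolescents | 59.1% | 34.6% |

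The cost is about 1 point only when control rates and true differences both match across age groups. The last two rows arise from allocation. Pooled MenACYW is 1350/2430 = 56% adults, while Menactra is 270/540 = 50%. At control 0.5/0.8 and -2 points in each age group:

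- MenACYW pooled: (1350 × 0.48 + 1080 × 0.78)/2430 = 1490.4/2430 = 0.613
- Menactra pooled: (270 × 0.5 + 270 × 0.8)/540 = 0.650
- Pooled difference: -3.7 points, against -2 in each age group

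The within-age comparisons do not carry this shift; a gate would impose it on them. With rates reversed (0.8/0.5) the pooled difference is 1571.4/2430 - 0.650 = -0.3 points, and the gate costs almost nothing.

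**The case for a change.** The best argument for acting is that a split result is plausible and its standing should be known beforehand. With an assumed control rate of 80%, adults equal, and adolescents 15 or 20 points lower in one serogroup, looking at that serogroup alone, the adult test passes while the pooled test fails in 55% or 90% of trials. The possibility is real, but the adult claim in those trials is true, and the written rule already answers the question: the objective is met when its four nulls are rejected.

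It also stands that the inflation is real in the worst case, and that no readable text orders the tests. The redacted sample-size text could contain an order, but that cannot be assumed.

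Two supporting points are weak. The registration sentence in the SAP Introduction describes the trial as a whole and does not mention age groups. SAP 5.1.4 repeats the age-group analyses on PPAS2 and FAS2 ("Non-inferiority of hSBA vaccine seroresponse rate for MenACYW conjugate vaccine (Groups 1b-3b pooled"), but the same list also repeats the descriptive Secondary Objectives 3 and 4, so it says nothing about claim status.

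Nor is one SAP sentence the whole cost. Protocol 12.1 does say that "the SAP will describe all analyses to be performed under the responsibility of the Sponsor and all the conventions to be taken", but it requires this to be in accordance with the protocol, and the protocol's rule has no gate. Aligning the two means an amendment, and Protocol 5.4 says "All substantial amendments (e.g., that affect the conduct of the trial or the safety of subjects) require IEC / IRB approval".

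**Conclusion.** The observation is correct, but no change to the plan follows. This is a fair trade-off. Each claim concerns its own population and is held near 2.5% one-sided by its own four-serogroup rule. Adults and adolescents do not overlap, so controlling error claim by claim is defensible. The excess, up to about 5.9-6.6% for any false Menactra claim, needs one serogroup exactly at the margin in both age groups with the rest sure to pass.

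The gate would remove age-group claims after a failed Primary Objective 2. It would not give joint control of the two claims, and it could withhold true ones: from about 1 point of power when the age groups behave alike to 24 or more when control rates or true differences diverge. The alternative, a sentence saying that error is controlled within each objective, would record what the rules already imply and alter no result.

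These figures assume control rates of 0.5-0.9, 10% loss in each age group and, for power, independent serogroups. The direction of the conclusion does not depend on one particular rate. The gate's cost does, and the documents do not show the rates needed to fix it.

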5.1.2.2.2 Statistical Methods

For the 4 non-inferiority hypotheses using the seroresponse rates, the CI of the difference in proportions will be computed for each of the serogroups A, C, Y, and W using the Wilson Score method without continuity correction (8). The statistical method as described in Section 5.1.1.2.2 will be used to Groups 1a - 3a pooled and Group 4a.

5.1.2.3 Secondary Objective 3

Comparison of 3 MenACYW Conjugate Vaccine Lots in Terms of hSBA Vaccine Seroresponse

5.1.2.3.1 Hypotheses

No hypotheses will be tested. Descriptive statistics will be presented.

5.1.2.3.2 Statistical Methods

The difference in percentages of subjects who achieve an hSBA vaccine seroresponse (as defined in Section 4.4.2.4) 30 days after the administration of MenACYW conjugate vaccine for meningococcal serogroups A, C, Y, and W in Groups 1, 2, and 3 will be calculated for each comparison and 95% CI will be provided.

The CI of the difference in proportions will be computed using the Wilson Score method without continuity correction (8).

5.1.2.4 Secondary Objective 4

Comparison of MenACYW Conjugate Vaccine to Menactra[®] in Terms of hSBA GMTs

5.1.2.4.1 Hypothesis

No hypotheses will be tested. Descriptive statistics will be presented.

5.1.2.4.2 Statistical Methods

The ratio of GMTs of meningococcal serogroups A, C, Y, and W between the MenACYW conjugate vaccine Groups 1- 3 pooled (Lots 1, 2, and 3 combined) and the Menactra[®] Group 4 30 days after the administration of vaccine will be calculated and 95% CI will be provided.

Assuming that \log_{10} transformation of the data follows a normal distribution, the \log_{10} (data) will be used for the statistical analysis, then antilog transformations will be applied to the results of calculations, in order to provide the results in terms of GMTs.

For each of the GMT ratios, the statistical methodology will be based on the use of the 2-sided 95% CI of difference in means of post-vaccination \log_{10} transformed titers between the 2 groups with normal approximation.

The 95% CI for the difference in $\log_{10}(\text{GMT})$ between Group 1-3 pooled (Lots 1, 2, and 3 combined) and Group 4 will be in the form:

$$\bar{X}_{123} - \bar{X}_4 \pm t(1 - \alpha/2, n_{123} + n_4 - 2) \cdot S \sqrt{1/n_{123} + 1/n_4}$$

where $\bar{X}_i = \log_{10}(\text{GMT})$ is the mean of $\log_{10}(\text{titer})$ of Group i ,

$S^2 = [(n_{123} - 1) S_{123}^2 + (n_4 - 1) S_4^2] / (n_{123} + n_4 - 2)$ is the pooled sample variance,

n_i and S_i^2 are the sample size and sample variance of Group i ,

$t(1 - \alpha/2, n_{123} + n_4 - 2)$ is the $100(1 - \alpha/2)$ percentile of the t -distribution with degrees of freedom $df = n_{123} + n_4 - 2$.

The 95% CI for the ratio of GMTs can be obtained by taking antilog transformations for the calculated 95% CI for the difference in $\log_{10}(\text{GMT})$.

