## 6.5 Randomization and Allocation Procedures

On the day of enrollment, subjects who meet the inclusion/exclusion criteria and sign the ICF (subjects aged 18 to 55 years) or sign the assent form and whose parent / guardian signs the ICF

---

a according to local regulations

(subjects aged 10 to 17 years) will be randomly assigned to Groups 1 through 4 in a 3:3:3:2 ratio, stratified according to age such that Groups 1, 2, and 3 will have approximately 900 subjects (400 subjects 10 to 17 years old and 500 subjects 18 to 55 years old) and Group 4 will have approximately 600 subjects (300 subjects 10 to 17 years old and 300 subjects 18 to 55 years old).

Site staff will connect to the IWRS, enter the identification and security information, and confirm a minimal amount of data in response to IWRS prompts. The IWRS will then provide the group assignment and have the site staff confirm it. The full detailed procedures for group allocation are described in the Operating Guidelines. If the subject is not eligible to participate in the trial, then the information will only be recorded on the subject recruitment log.

Subject numbers that are assigned by the IWRS will consist of an 8-digit string (a 3-digit trial center identifier and a 5-digit subject identifier connected by “-”). For example, Subject 001-00001 is the first subject enrolled in center number 1. Subject numbers should not be reassigned for any reason.

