#### *Comparison of MenACYW Conjugate Vaccine to Menactra® in Terms of hSBA GMTs*

The ratio of GMTs of meningococcal serogroups A, C, Y, and W between the MenACYW conjugate vaccine Groups 1- 3 pooled (Lots 1, 2, and 3 combined) and the Menactra® Group 4 30 days after the administration of vaccine will be calculated and 95% CI will be provided.

Assuming that  $\log_{10}$  transformation of the data follows a normal distribution, the  $\log_{10}$  (data) will be used for the statistical analysis, then antilog transformations will be applied to the results of calculations, in order to provide the results in terms of GMTs.

For each of the GMT ratios, the statistical methodology will be based on the use of the 2-sided 95% CI of difference in means of post-vaccination  $\log_{10}$  transformed titers between the 2 groups with normal approximation.

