3.1 Trial Design

This is a Phase III, modified double-blind, randomized, parallel-group, active-controlled, multi-center study to evaluate immune lot consistency of MenACYW conjugate vaccine, evaluate the immune non-inferiority versus Menactra[®], and describe the safety and additional immunogenicity of these study vaccines in adolescents and adults aged 10 to 55 years in the United States.

Healthy, meningococcal-vaccine naïve adolescents and adults will be randomized in a 3:3:3:2 ratio to the following groups:

- Group 1: MenACYW conjugate vaccine (Lot 1)
 - Group 1a: 400 subjects 10 to 17 years of age
 - Group 1b: 500 subjects 18 to 55 years of age
- Group 2: MenACYW conjugate vaccine (Lot 2)
 - Group 2a: 400 subjects 10 to 17 years of age
 - Group 2b: 500 subjects 18 to 55 years of age
- Group 3: MenACYW conjugate vaccine (Lot 3)
 - Group 3a: 400 subjects 10 to 17 years of age
 - Group 3b: 500 subjects 18 to 55 years of age
- Group 4: Menactra[®]
 - Group 4a: 300 subjects 10 to 17 years of age
 - Group 4b: 300 subjects 18 to 55 years of age

All subjects will provide blood samples for immunogenicity assessment at baseline (pre-vaccination) and at 30 to 44 days post-vaccination.

Solicited adverse event (AE) information will be collected for 7 days after vaccination, unsolicited AE information will be collected from Visit 1 (Day [D] 0) to Visit 2 (D30 [+14 days]), and serious adverse event (SAE) information will be collected from D0 through D180 (+14 days) after vaccination.

Medically-attended adverse events (MAAEs) information will be collected throughout the study from Visit 1 to Visit 2 (as part of the collection of unsolicited AE information) and from Visit 2 through D180 (+14 days) (as MAAEs).

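### The Secondary Objective 4 GMT ratio omits the age stratum used in randomisation, and Protocol 6.5 does not say whether its age cells are rounded figures or enforced targets

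*SAP*

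**What the plan says.** Protocol 6.5 has subjects "randomly assigned to Groups 1 through 4 in a 3:3:3:2 ratio, stratified according to age such that Groups 1, 2, and 3" reach about 900 each and Group 4 about 600. The age counts stand in the same sentence: "400 subjects 10 to 17 years old and 500 subjects 18 to 55 years old) and Group 4 will have approximately 600 subjects", the latter split 300 and 300. The synopsis, Protocol 5.1.1 and SAP 3.1 repeat these cells; SAP 3.1 introduces them with "adolescents and adults will be randomized in a 3:3:3:2 ratio to the following groups". On the mechanism, Protocol 6.5 says only: "The full detailed procedures for group allocation are described in the Operating Guidelines".

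Secondary Objective 4 compares hSBA GMTs between the pooled MenACYW lots and Menactra. Protocol 12.1.2.4 says: "For each of the GMT ratios, the statistical methodology will be based on the use of the 2-sided 95% CI of difference in means". SAP 5.1.2.4.2 writes this out: the interval for the log10 GMT difference "between Group 1-3 pooled (Lots 1, 2, and 3 combined) and Group 4 will be in the form" of a pooled-variance t interval on log10 titers with no stratum term. SAP 5.1.2.4.1 gives its status: "No hypotheses will be tested. Descriptive statistics will be presented".

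SAP 5.1.4 plans hSBA GMTs with 95% CIs by age group for each vaccine group, for Appendix 15 of the study report. It lists no MenACYW/Menactra GMT ratio within age group or adjusted for age.

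**The concern.** Read literally, the printed cells are 4:4:4:3 in adolescents and 5:5:5:3 in adults. Only the totals are 3:3:3:2. If the randomisation system enforced those cells, the pooled MenACYW arm and the Menactra arm differ in age mix by design. A crude ratio of pooled GMTs would then mix the vaccine contrast with any age effect on titer, and a larger sample would not remove this.

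The estimate and interval for Secondary Objective 4 are at stake. This is the only planned MenACYW-versus-Menactra comparison of GMTs. Seroresponse is compared pooled and also within adults and within adolescents (Secondary Objectives 1 and 2); the GMT ratio has no such age-specific version.

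**Working it through.** **Inputs.** From Protocol 6.5: cells of 400 + 500 in each lot group and 300 + 300 in Group 4. From the synopsis: 10% dropout, 810 evaluable per lot, and for Menactra "planned = 600 (evaluable = 540". Assumed, because the documents give neither: the adolescent/adult GMT ratio f, and a within-age SD of 0.4 to 0.8 on the log10 scale. Dropout is taken as equal across cells.

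**1. The plan's own totals.** 3 × 900 + 600 = 3300, and 900:900:900:600 is 3:3:3:2. Evaluable: 900 × 0.9 = 810 and 600 × 0.9 = 540, as printed. Pooled MenACYW evaluable: 3 × 810 = 2430.

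**2. Two readings of the cells.** Both have 1500 adolescents and 1800 adults.

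| Reading | Adolescents, Groups 1/2/3/4 | Adults, Groups 1/2/3/4 | Adolescent share, pooled MenACYW vs Menactra |
|---|---|---|---|
| Printed cells enforced | 400/400/400/300 | 500/500/500/300 | 1200/2700 = 44.4% vs 300/600 = 50.0% |
| 3:3:3:2 within strata | 409/409/409/273 | 491/491/491/327 | 45.5% vs 45.5% |

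The second row is 1500 × 3/11, 1500 × 2/11, 1800 × 3/11 and 1800 × 2/11. Rounded to the nearest hundred, it becomes the first row exactly. Both rows have arm totals of 900 and 600, so the totals cannot tell them apart.

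**3. Shift if the cells are enforced.** The share difference is 4/9 − 1/2 = −1/18. With the same f under both vaccines, the crude log10 difference moves by −(1/18) × log10 f, so the ratio is multiplied by f^(−1/18).

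| Age fold-difference | Adolescents higher | Adults higher | Shift in SE, SD 0.4 to 0.8 |
|---|---|---|---|
| 1.5 | 0.978 | 1.023 | 0.51 to 0.26 |
| 2 | 0.962 | 1.039 | 0.88 to 0.44 |
| 3 | 0.941 | 1.063 | 1.39 to 0.70 |

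Here SE = SD × √(1/2430 + 1/540) = 0.04757 × SD, that is 0.0190 to 0.0381. At a 2-fold difference the shift is 0.3010/18 = 0.0167 log10. The 95% CI half-width is about 9% to 19% on the ratio scale over the same SD range.

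**4. Interval coverage at f = 2, cells enforced.** Coverage = Φ(1.96k − s) − Φ(−1.96k − s), where s is the shift in SE and k is the SD including age variation divided by the within-age SD. At SD 0.4, k = √(0.16 + 0.2475 × 0.301²)/0.4 = 1.068 and s = 0.88, giving 0.886. At SD 0.8, coverage is 0.933. Nominal is 0.95.

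**5. Cost of a stratum term.** Evaluable cells are 1080 vs 270 adolescents and 1350 vs 270 adults. Precisions are 1/(1/1080 + 1/270) = 216 and 1/(1/1350 + 1/270) = 225, total 441, so SE = SD/√441 = 0.04762 × SD. Against 0.04757 that is +0.09% if age has no effect. At f = 2 and SD 0.7, the model SE is 0.0333 against a crude SE of 0.0341, about 2.1% lower.

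**The case against.** The strongest reply is that there is no imbalance. A ratio stratified by age most naturally means 3:3:3:2 within each stratum, with planning counts rounded to hundreds, and Protocol 6.5 calls its group sizes approximate. On that reading the shift is zero. A reader might infer that 6.5 contradicts itself; the documents do not support this, because the within-stratum figures round to the printed cells exactly. Nor do they exclude enforced cells: the same counts appear in four places as group definitions, and the deciding detail is in the Operating Guidelines, which are outside these documents. This part of the objection stands to the extent that the imbalance is possible, not shown.

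Second, the ratio carries no hypothesis or margin, and Protocol 5.1.2 prefers seroresponse as the measure of vaccine performance. That stands, and it limits the weight of the point. A descriptive objective still delivers an estimate and an interval, and both should describe the vaccine contrast alone.

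Third, Appendix 15 will give GMTs with CIs by age group. With those and the group sizes, a reader could reconstruct within-age ratios and their intervals. That also stands: the information is planned, but the ratio itself is not.

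**Conclusion.** The point holds in a limited form. The Secondary Objective 4 ratio does not use the factor on which randomisation was stratified, and the visible text does not say whether the age cells are rounded or enforced. Two conditions are needed for any shift: enforced cells and GMTs that differ by age. Neither is established. If both hold with a 2-fold age difference, the ratio moves by about 4% in either direction, less than one SE over the assumed SD range. A 3-fold difference moves it by about 6%, which exceeds one SE only towards the low end of that range.

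A reader might infer that the primary objectives are compromised. The documents do not support that. All three lots have the same planned age mix under either reading, so the lot comparisons are unaffected and their decision rule needs no change. With enforced cells, the pooled seroresponse difference of Primary Objective 2 would carry the same mix difference. That is 0.0556 × 10 = about 0.6 percentage points for an assumed 10-point age difference in seroresponse, against a 10-point margin, and Secondary Objectives 1 and 2 test seroresponse within age. No success decision rests on the GMT ratio.

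**What to change.** In SAP 5.1.2.4.2 and Protocol 12.1.2.4, estimate the ratio and its 95% CI for each serogroup from a linear model on log10 post-vaccination titer with vaccine group and randomisation age stratum. Show the adolescent and adult ratios with CIs beside it, so that a vaccine-by-age difference is visible. Keep the crude ratio as supportive. Settle this before database lock, while the sponsor is still blinded.

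In Protocol 6.5, state whether the age cells are rounded figures or targets enforced by the randomisation system, and report the realised adolescent share in each arm.

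The cost is one term per serogroup plus matching text. No new data are needed and no subject is lost, because the stratum is known at randomisation. The model removes an age-mix shift if the cells were enforced, and costs almost nothing in precision if they were not.
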